- No existing catheter
- Renal disease (eGFR < 60)
- Liver disease (bilirubin greater than 3)
- Thyroid disorders (thyroid disease which currently requires treatment)
- Cancer
- HIV*
- Pregnancy (as determined by routine admission labs)

* Previously known HIV+ status. An HIV test will not be administered for the purpose of this study.

To ensure the safety of all patients, once every 2 weeks, blood samples will also be sent to the Massachusetts General Hospital Chemistry lab for analysis of selenium levels. If the selenium level is greater than 100 ug/dL the patient will be immediately removed from the study.

If the selenium level is greater than 100 ug/dL the subject will be immediately removed from the study.

If a patient decided to withdraw from the study or meets the exclusion criteria during the study, he/she will be removed from the study immediately. No further study procedures, including supplementation and blood and urine collection, will be completed. However, these subjects will be followed for 2 weeks for any adverse events related to the study. Neurological status, per routine care from the medical team, will be assessed. Additionally, lab values will be followed (if available from routine care) (complete blood count, serum creatinine, aspartate aminotransferase, alanine aminotransferase, alkaline phosphatase, total bilirubin, coagulation studies). Ongoing adverse events thought to be study drug related will be followed until resolution or the condition stabilizes.

IV. Subject Enrollment

All eligible subjects will be screened using the inclusion/exclusion criteria by the Clinical Research Nurse or Clinical Research Specialist, who will serve as the primary investigator. Assessment of potential eligibility of subjects will be provided by the primary physician. Subsequently, only members of the study staff can initiate the recruitment process. The consent and assent will only be obtained by members of the study staff who are a physician, a PhD, or an RN.

Following patient admission and stabilization, if the patient meets the inclusion criteria, a member of the clinical staff will approach the subjects/parents/guardian/ to gain permission for the study staff to discuss the study. If permission is granted, an appropriate member of the study staff will approach

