All patients will receive routine nutrition support that includes oral, enteral, or parenteral nutrition or a combination of the 3 sources. All enteral nutrition products contain Se in the form of sodium selenate (Table 2). All patients who require parenteral nutrition receive 20 ug of IV selenious acid per day (this is standard therapy at SBH). According to our previous study, despite various routes of nutrition support within and among subjects, Se intake remained stable throughout the 8 week time period and cover approximately 150 – 200% of the RDA for Se. Therefore standard nutrition support, including Se, should not interfere with this proposed investigation (Figure 1).

In addition to standard nutrition support, all patients will be randomized to receive IV Se supplementation or placebo. The placebo (0.9% sodium chloride or 5% Dextrose solution, depending on the clinical situation) will look identical to the Se supplements. Patients in the experimental groups will receive parenteral Se as selenous acid (added to 25 ml of 5% Dextrose solution or 0.9% sodium chloride) (carrier solution will depend on clinical situation) as a 24-hour continuous infusion in doses 2 ug/kg/day (n = 25), or 4 ug/kg/day (n = 25). The placebo group (n = 25) will receive sodium chloride 0.9% in the same regimen. These Se supplement amounts were determined taking into account previous studies in the literature, current RDAs, UTLs, ASPEN guidelines for parenteral Se, and dietary data recorded from our previous study. According to reference weights adapted from NHANES III data, supplement doses (2 ug/kg/day and 4 ug/kg/day) do not exceed the upper tolerable limits for children.

The Se/Placebo will be provided as a 24-hour continuous infusion. The continuous infusion of Se/Placebo may be temporarily interrupted, if necessary, for reasons including, but not limited to, surgical procedures and drug compatibility issues. These temporary interruptions will not reduce the integrity of

the study. However, if the Se/Placebo infusion is held for longer than 48 consecutive hours or 72 hours in 7 days then the subject will be removed from the study. At this time no further study drug will be given or biological samples taken. All subjects will be monitored for any treatment-related adverse events for 2 weeks following discontinuation of the study therapy.

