Prior to initiation of the study, the research nurse will hold an in-service for clinical staff to alert them of the study. A specific research sticker will be placed in the chart to alert clinical staff that the patient is enrolled in this research study. The MD responsible for the care of the patient will write the orders for the supplements. The Pharmacy will prepare all supplements and the nurses will administer them.

C. Data Collection

Plasma and urine Se and plasma Gpx will be measured weekly from the time of admission for a maximum of 8 weeks or until the patient achieves 95% definitive wound closure.

The research nurse will obtain 4 ml or 8ml (8 ml will be drawn instead of 4 ml every other week starting with week 1 for real time analysis) of whole blood off an existing catheter and place it into a trace-element free blood collection tube.

Every other week, when 8 ml of blood is needed, 4 ml will be transferred by the unit assistant to the MGH laboratory for immediate analyses (the MGH lab uses Quest Labs for analysis of selenium). If in the unlikely event that the MGH lab rejects the sample for any reason, another 4 mL blood draw will be collected and sent to the MGH lab for real-time analyses.

Weekly, the 4 ml sample will be transported by the nurse to the clinical research lab (in the same building). In the lab the nurse will use a centrifuge to separate the blood and then pipette the plasma and whole blood into collection vials to be frozen prior to analyses. A 24 hour urine will be initiated the day prior to blood sampling for analysis of urinary Se. Urine will be collected via an existing catheter. If no catheter exists patient will be asked to urinate into a container. If the patient is unable to urinate into a container, the urine sample will not be collected. Infant urine will be collected via diapers. The research nurse will then bring the urine container down to the clinical research lab and aliquot it into 50 ml vials prior to being frozen. Frozen samples are eventually mailed to a commercial laboratory for lab analyses. The PI is certified to ship biological products and all appropriate regulations will be followed.

Culture Data

Wound cultures will be obtained for all patients admitted to the acute care unit at Shriners Burns Hospital, per routine care, on admission. Urine cultures will also be obtained upon admission if one or more of the following criteria are met:

- Symptoms of urinary tract infection (UTI)

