The pathogenic fungi (Histoplasma and Blastomyces) cultures will be referred to the MGH laboratory for speciation. Results are confidentially reported to the medical team at Shriners Burns Hospital.

Normal flora cultured from the sputum (viridians strep Neisseria species, coagulase negative Staphylococcus and rare amounts of yeast, enteric gram negatives, Staph. aureus.) will be documented as normal flora)

Dietary Data

Dietary data (enteral nutrition, parenteral nutrition, oral intake) will be collected daily from the medical record. Total Se intake via supplements and/or enteral feedings will be calculated based on daily intake and output sheets as recorded by the bedside nurse. Dietary Se intake from food will be determined using the Nutrient Database System for Research version 2005.

Other Data

Weights will be obtained as part of routine care by the bedside nurse, and recorded twice a week. Demographic data will be obtained from the medical record. Please see data collection sheet for details.

As part of routine care by the medical team neurological status will be assessed and several laboratory values will be monitored closely (including total protein, albumin, prealbumin and C-reactive protein complete blood count, serum creatinine, AST, ALT, alkaline phosphatase, total bilirubin, and coagulation studies) will be recorded from the medical record.

D. Selenium Analysis

Blood (4 ml or 8 ml) and urine samples will be obtained weekly. De-identified samples will be sent to a commercial laboratory for analyses. Results will be sent to Shriners Burns Hospital in Boston. Additionally, to ensure the safety of all patients, once every 2 weeks, blood samples (4 ml) will also be sent to the Massachusetts General Hospital Chemistry lab for analysis. These results are typically available after 24-48 hours.

The study endpoint will be whichever of the following factors happens first:

- 8 weeks
- discontinuation of central venous catheter
- a stop in Se/Placebo infusion lasting longer than 48 consecutive hours or 72 hours in 1 week,
- when the patient achieves 95% definitive wound closure determined by the attending physician.

No interim analyses are planned. Data obtained from our previous investigation on Se and pediatric burns was used for the power analysis calculation:

$$n = (2 \times [Z_{(1-\alpha/2)} + Z_{(1-\beta)}]^2) / \Delta^2$$

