where $Z_{(1-\alpha/2)}$ and $Z_{(1-\beta)}$ represent percentage points of the normal distribution for statistical significance level and power, respectively. The values used were 1.96 for a significance level of 5% and 0.8416 for a power of 80%. The Δ represents the standardized difference (the treatment difference divided by its standard deviation). This was calculated by subtracting the mean plasma Se determined in our pilot study (1.08 $\mu\text{mol/L}$) from the average plasma Se of healthy American children 1.35 ($\mu\text{mol/L}$) and dividing by the standard deviation (0.34). This calculation revealed that 25 subjects are needed per group to obtain 80% power and a significance level of 5%.

All subjects enrolled will be included in the statistical analyses (intent-to treat). A 2-sided statistical test will be used for all analyses and the overall type-I error rate will be controlled at the 5% level. For each dependent variable (plasma selenium, urinary selenium, plasma GPx activity) a 2-way repeated measures ANOVA will be used to examine the difference among groups and over time (primary hypothesis). Tukey's will be utilized as the post-hoc test.

An ordinal logistic regression will be performed to determine the relationship between the incidence of infection (categorized by burn, bloodstream, urinary tract infection, and PNA) and plasma selenium, urinary selenium, plasma GPX, age, initial percent TBSA burned, and treatment group (secondary hypothesis).

Appropriate confounding factors (including but not limited to dietary Se intake, age, sex, race, initial %TBSA, and length of time from burn injury to study enrollment) will be included in the statistical models. All statistics will be completed using SAS software.

VI. Risks and Discomforts

Phlebotomy will be minimal (4 or 8 ml/wk) and will be obtained painlessly through existing catheters or during operative procedures.

Se toxicity is rare. Symptoms include:

- memory loss
- gastrointestinal upset,
- hair loss,
- weakened nails,
- white blotchy nails,
- garlic breath odor,
- metallic taste,
- vomiting,

- sweat
- dermatitis,
- dental defects,
- nervousness,
- mental depression,
- fatigue,
- irritability,
- mild nerve damage,
- Peripheral vascular collapse,
- Internal vascular congestion,
- Hemorrhage,
- Congested and edematus lungs,
- Brick-red color gastric mucosa
- Coma
- Death

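### Infection has no defined observation window: event-driven stopping gives unequal, probably informative follow-up, and the infection model contains no time observed

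*Combined protocol and SAP*

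**What the plan says.** **End of participation.** Section V.D states: "The study endpoint will be whichever of the following factors happens first". Besides 8 weeks, the events are "discontinuation of central venous catheter", "a stop in Se/Placebo infusion lasting longer than 48 consecutive hours or 72 hours in 1 week" and "when the patient achieves 95% definitive wound closure determined by the attending physician". Section V.B applies the same infusion limits and makes removal the consequence. Section III adds that a child who "meets the exclusion criteria during the study, he/she will be removed from the study immediately"; the exclusion list includes no existing catheter, eGFR below 60 and bilirubin above 3.

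**After removal.** Section III stops study procedures, and V.B stops study drug and biological samples. Sections III, V.B and VIII then provide 2 weeks of follow-up for study- or treatment-related adverse events. Section III names the routine-care data to be followed (neurological status and a list of laboratory values). Cultures and infections are not among them.

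**Start of observation.** Section V.C says "Plasma and urine Se and plasma Gpx will be measured weekly from the time of admission for a maximum of 8 weeks", or until 95% closure. That sentence covers biomarkers only. Children may enrol up to 3 weeks after the burn (section III), and wound cultures begin on admission (V.C). Nothing separates infections that began before the first infusion from later ones.

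**Analysis.** The end of section V.D promises: "All subjects enrolled will be included in the statistical analyses (intent-to treat"). Infection is analysed by ordinal logistic regression on plasma Se, urinary Se, plasma GPx, age, initial %TBSA and treatment group. An open-ended confounder list adds, among others, time from burn to enrolment. Time observed appears in neither list.

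**The concern.** A count, or a yes/no, for infection depends on how long the child is watched. Here that length is set by events after randomisation: healing, line removal, infusion interruption, and renal or hepatic values. Some of these may follow from infection and others mark recovery. If selenium affects any of them, the arms differ in their opportunity to have an infection counted.

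The biomarker association is more exposed still. It compares children by Se status rather than by assigned arm, so randomisation gives it no protection against a link between Se status and length of observation.

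Finally, if infection is counted only while the child is on study, all 75 children enter the analysis but each contributes infection data only until drug, line or eligibility is lost. That weakens the intent-to-treat comparison for infection, though it excludes nobody.

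**Working it through.** **The plan's own figure.** The only sample-size calculation is for plasma Se: n = 2 × (1.96 + 0.8416)² / (0.27/0.34)² = 24.89, rounded up to 25 per group. It reproduces and is not affected by this point. The plan gives no infection rate, window length or removal rate, so everything below is illustration.

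**1. How unequal windows could be.** Table 4 gives a pilot stay of 50 ± 40 days, range 11 to 161. Stay is not the observation window, but a child with the shortest pilot stay against the 8-week maximum gives 56/11 = 5.1.

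**2. Effect of window length alone.** Assume a constant rate r. Then P(at least one) = 1 − exp(−r × days), and odds = P/(1 − P). The rates and windows are assumptions; 2 per 30 days is the supplemented-group figure from the adult burn trial in Table 7 that counted infections over the first 30 days.

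| Assumed rate | P, 14 d | P, 56 d | Odds ratio, 56 v 14 d | P, 28 d | P, 35 d | Odds ratio, 35 v 28 d |
|---|---|---|---|---|---|---|
| 1 per 56 d | 0.221 | 0.632 | 1.718/0.284 = 6.1 | 0.393 | 0.465 | 0.868/0.649 = 1.3 |
| 1 per 30 d | 0.373 | 0.845 | 5.467/0.595 = 9.2 | 0.607 | 0.689 | 2.211/1.543 = 1.4 |
| 2 per 30 d | 0.607 | 0.976 | 40.82/1.543 = 26 | 0.845 | 0.903 | 9.312/5.467 = 1.7 |

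The 56 v 14 day column compares two children. The 35 v 28 day column compares two arms with no drug effect.

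**3. If an infection can end participation.** Suppose each infection ends observation with probability q, up to T = 56 days. Expected days observed are (1 − exp(−q r T))/(q r), and the expected count is r times that. With a true rate ratio of 0.50, the ratio of observed counts is (1 − exp(−q r T/2)) / (1 − exp(−q r T)), where r is the control rate:

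- r = 4 per 30 days: 0.59 (q = 0.10), 0.72 (q = 0.25), 0.87 (q = 0.50).
- r = 2 per 30 days: 0.55, 0.61, 0.72.

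Crude counts are pulled toward no difference. Infections per patient-day stay at 0.50, but only because this model has constant rates and stopping that depends on nothing except the observed infection.

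**4. Which children lose follow-up?** Take sicker children at 4 per 30 days who otherwise run to 56 days, and less sick children at 2 per 30 days with an assumed mean of 21 days to closure or line removal. Total stopping hazards are q × 4/30 and 1/21 + q × 2/30, and mean days are (1 − exp(−hazard × 56))/hazard:

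| q | Sicker, days | Less sick, days |
|---|---|---|
| 0 | 56 | 20 |
| 0.10 | 39 | 18 |
| 0.25 | 25 | 15 |
| 0.50 | 15 | 12 |
| 1 | 7.5 | 8.7 |

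The sicker children keep the longer window unless nearly every infection ends participation. The direction turns on quantities that the documents do not give.

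**The case against.** **Silence is not a stop rule.** No sentence says that infection recording ends at the study endpoint. What stops explicitly is drug, sampling and study procedures. Infection data come from routine care, with cultures at least weekly, so recording could continue. This stands: the end of infection recording is an inference. But nothing says recording continues either, and the window is undefined on both readings.

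**A reader might infer that follow-up is cut short in the sickest children because sepsis triggers removal.** The documents do not support this. They link no stop event to infection, give no frequencies, and name only surgery and drug compatibility as examples of reasons for infusion interruption. Wound closure and elective line removal shorten follow-up in healthier children, and step 4 mostly runs against the claim.

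**The illustrations are limited.** A child removed because of an infection already has one, so the chance of at least one is unaffected by that mechanism; only later infections are lost. Differences in baseline prognosis are balanced in expectation by randomisation, and the same stopping rules apply blind in all arms. A 7-day difference between arms has no source in the protocol. All of this stands. It does not protect the arm comparison if treatment changes stopping, or the biomarker association at all.

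**Covariates help in part.** Adjustment for %TBSA, age and time from burn to enrolment addresses some of the late entry. It replaces neither time observed nor a rule on infections that began before the first infusion.

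**Conclusion.** The point holds as a gap in definition and method. Infection has no stated start, end or denominator; participation ends at the first of several events after randomisation; and the model has no exposure time. Follow-up will be unequal and is probably informative, possibly in both directions. The sign and size of the net bias cannot be derived from the documents.

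The odds ratios of about 9 (14 v 56 days) and 1.4 (35 v 28 days), and the attenuation of a true 0.50 to between 0.55 and 0.87, show what is possible under assumed rates, windows and removal probabilities. They are not estimates for this trial. A reader might also infer that the plan contradicts its intent-to-treat statement. It does not: all enrolled children are analysed, and the comparison is weakened only if infections are counted solely while on study. The primary biomarker hypothesis and the 25 per group are untouched. The change is worth making because it is cheap.

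**What to change.** Leave all treatment-stopping rules as they are, and separate them from infection follow-up:

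- For every randomised child whose family has not withdrawn consent, record routine-care infections from first infusion to a fixed 8 weeks, regardless of drug, line or eligibility status. Stop at discharge only if no later data are available.
- List infections present before the first infusion separately.
- Record days observed and the reason for stopping.
- Compare arms by infections per patient-day, using a count model with log days as offset.
- As sensitivity analyses, give an on-treatment version and a check for informative stopping.

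The fixed window matters more than the offset. An offset corrects for length, but if the infection rate changes over time it does not make a short early window comparable with 8 full weeks. Discharge is itself related to outcome, so its use as an end date should be reported by arm. Biomarker–infection associations would remain limited to the period with samples. The lists of events that end observation in sections III, V.B, V.C and V.D should also be reconciled.

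Cost: protocol wording and extra chart review, with no new samples or procedures, since cultures and diagnoses come from routine care. Counting off-drug infections dilutes the contrast slightly; the on-treatment analysis shows by how much.

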Berger et al. 2006 (34)	Combination of 2 randomised, double-blind trial	41 burn patients with mean TBSA of 46%	IV trace element cocktail vs Placebo. Cu: 2.5-3.1 mg/d Se: 315-380 ug/d Zn: 26.2-31.4 mg/d	8-21 days	Plasma Se levels increased with supplementation; Reduced number of infections in supplemented pts (3.5 vs 2 episodes per pt)
Berger et al. 2007 (53)	Prospective, randomized, placebo-controlled trial	21 burn patients with mean TBSA of 45%	IV trace element cocktail vs Placebo. Cu: 3.75 mg/d Se: 375 ug/d Zn: 37.5 mg/d	14-21 days	Plasma Se sig higher in supplement group; Number of infect in first 30 days was sig lower in supplement group (2 vs 4 infections per

					pt); Supplement group had fewer regrafting episodes.
Berger et al. 1998 (36)	Prospective, randomized, placebo-controlled trial	20 burn patients with mean TBSA of 48%	IV trace element cocktail vs Placebo. Cu: 3.75 mg/d Se: 375 ug/d Zn: 37.5 mg/d	8 days	The number of infections were lower in supplement group

Overall the data among adults is promising, but does not identify a specific guideline for selenium supplementation during critical illness. The data among children is scarce and less impressive.

C. Rationale behind proposed research/ benefits to society

The Se status of children with major burns is suboptimal which may increase the incidence of infection. Se requirements during critical illness are not known. Results from this investigation may provide a tool for recommending Se supplements during burn injury.

II. Specific Aims

The hypothesis of this research is that Se supplementation will restore the depressed Se status among children with burn injuries. The secondary hypothesis is that Se status is related to the incidence of infection among pediatric patients with burns.

The specific aims of this research are

1. to determine the impact of supplemental Se needed on plasma Se, Gpx activity, and urine selenium among pediatric patients with burns $\geq 20\%$ TBSA.
2. to determine the association between Se supplementation, biomarkers of Se status and indicators of stress and infection.

III. Subject Selection

All subjects (n = 75) will be recruited from the Shriners Hospital for Children in Boston.

Inclusion Criteria:

- Between 1 and 18 years of age admitted to Shriners Burns Hospital
- TBSA burn of $\geq 20\%$
- Existing catheter
- Enrolled into study within 3 weeks of burn injury

Exclusion Criteria:

- < 1 year or > 18 years of age
- $< 20\%$ TBSA burn

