subjects/parents/ guardians at the bedside, who meet the inclusion/exclusion criteria, with a brief explanation of the study. A more detailed explanation will be offered in a private room to those interested in participation. The alternative to participation is “not to participate”. Care will not be altered for patients who do not participate. Informed consent will be obtained if the patient and/or parent/legal guardian agrees to participate. Parents/legal guardians will be allowed an indefinite amount of time for questions and participation consideration. Parents/legal guardian will provide consent for 0-18 year old children (documented in writing using the PHRC approved consent form). The permission of both parents is required unless one parent is deceased, unknown, incompetent, or not reasonably available or if only one parent has legal responsibility for the care and custody of the child. Any child 14 years or older, who is able, will consent along with parent/guardian. The assent of each child (age 7 and older) who is capable of providing assent based on medical condition, age, maturity, and psychological state will be sought. According to a power analysis calculation, 75 children will be included in this study.

B. Treatment Assignment and Randomization

This is a randomized, double-blind, placebo-controlled trial. Patients will be randomly assigned to receive Selenium supplementation (either 2, or 4 ug/kg/day) or a placebo. 25 subjects will be in each group (total of 75 subjects). Randomization will occur by using a computerized randomization list. A pharmacist, who is not a member of the study staff, will prepare the supplements and label them accordingly prior to distribution.

V. Study Procedures

A. Study Parameters

- B. Lab studies conducted solely for the purpose of this study include plasma and urinary Se, plasma Gpx and dietary Se intake. Other parameters that will be included are demographics, medications, wound debridement procedures, invasive devices, mode of nutrition support, kilocalorie and protein intake, weekly weights, neurological status (as routinely assessed by the clinical team) and routine laboratory studies.

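### The stated 80% power belongs to one unadjusted two-group comparison of single values, not to the planned three-arm repeated measures ANOVA with Tukey tests

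*Combined protocol and SAP*

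**What the plan says.** All points are in the combined protocol and SAP.

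- **Sizing (V.D, power analysis).** The formula is n = 2(z for alpha + z for power)² / Δ², with 1.96 and 0.8416. Δ is the healthy-child mean plasma selenium (1.35 µmol/L) minus the pilot mean (1.08), divided by an SD of 0.34. The conclusion reads "This calculation revealed that 25 subjects are needed per group to obtain 80% power and a significance level of 5" per cent.
- **Arms (IV.B).** There are two selenium doses and placebo: "25 subjects will be in each group (total of 75 subjects").
- **Hypothesis (II).** "Se supplementation will restore the depressed Se status among children with burn injuries". No dose is named.
- **Primary analysis (V.D).** For each of three biomarkers, "a 2-way repeated measures ANOVA will be used to examine the difference among groups and over time (primary hypothesis"). Then: "Tukey's will be utilized as the post-hoc test". For error control, "the overall type-I error rate will be controlled at the 5% level".
- **Sampling (V.C).** "Plasma and urine Se and plasma Gpx will be measured weekly from the time of admission for a maximum of 8 weeks", or until wound closure.
- **Early end of sampling (V.B).** After a long interruption of the infusion the child is removed: "At this time no further study drug will be given or biological samples taken". V.D lists further events that end participation before 8 weeks.

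**The concern.** The sizing formula has no term for a third arm, for multiplicity or for repeated measurement. The planned analysis has all three. The text does not link the 80% to the omnibus group test, to a dose-placebo contrast, to a number of visits or to a within-child correlation.

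With two active doses, whether the groups differ and whether a given dose differs from placebo are separate questions with different power. As the text stands, a reader cannot tell which one has 80%. The practical risk comes at interpretation: someone who believes that each dose had 80% power against placebo may take a non-significant Tukey result as stronger evidence of no effect than it is.

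**Working it through.** **Inputs.** Means 1.08 and 1.35, SD 0.34, z-values 1.96 and 0.8416 (V.D); 25 per arm, three arms (IV.B). Assumptions needed to stay on the sizing basis: one value per child, equal variances, normality, no covariates, no losses.

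**1. The plan's own figure.** Δ = 0.27/0.34 = 0.794, and Δ² = 0.631.
n = 2 × (1.96 + 0.8416)² / 0.631 = 2 × 7.849 / 0.631 = 24.89, so 25 per group. The figure reproduces. With 25 per group the noncentrality is 0.794 × √(25/2) = 2.808, and the z-test power is 80.2%. With a t-test it is 78.6% (two groups only, 48 df) or 79.1% (error variance from all three arms, 72 df).

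**2. One dose against placebo under Tukey.** Error df = 3 × 24 = 72. The critical value is q(0.95; 3, 72)/√2 = 3.384/√2 = 2.393, where an unadjusted t-test with 72 df uses 1.993. A noncentral t with noncentrality 2.808 and 72 df gives power **66.1%**.

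**3. Omnibus group test.** F with 2 and 72 df, critical value 3.124, noncentrality λ = 25 × Σ(standardised mean − grand mean)².

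| True means (placebo / lower / higher dose) | λ | Power |
|---|---|---|
| 1.08 / 1.35 / 1.35 | 25 × (2/3) × 0.631 = 10.51 | **81.9%** |
| 1.08 / 1.08 / 1.35 | 10.51 | **81.9%** |
| 1.08 / 1.215 / 1.35 | 25 × (1/2) × 0.631 = 7.88 | **69.1%** |

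**4. Tukey with both doses fully effective** (200,000 simulated trials, same basis). At least one dose is separated from placebo in 81.0% of trials, and both doses in 51.1%.

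**5. Why these are not the power of the planned analysis.** That power depends on the within-child correlation ρ, on the number and timing of visits, and on whether 0.34 is the SD of single samples or of child means. The documents give none of these. To show how far the answer can move, assume that 0.34 is a single-sample SD, that correlation is equal between visits, and that four visits are used. Power for one fully effective dose under Tukey is then:

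| Contrast | ρ = 0.3 | ρ = 0.9 |
|---|---|---|
| Mean of 4 visits, all showing the effect | 95% | 70% |
| Mean of 4 visits, one of them pre-treatment | 74% | 42% |
| Mean of 3 later visits minus baseline | 70% | over 99% |

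Even the direction of the dependence on ρ changes with the contrast. If 0.34 is instead the SD of child means, averaging adds nothing and the 66% stands before covariates and losses. These rows are illustrations under assumptions, not estimates of this trial's power.

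**The case against.** The best defence is that the plan assigns its primary hypothesis to the ANOVA and calls Tukey a post hoc test, that the hypothesis names no dose, and that nowhere is 80% claimed for each dose. On the sizing basis the omnibus test has about 82% if both doses, or only one, have the full effect. This stands: 80% is about right for the omnibus group test under full effect. The 69% requires an assumed half effect at the lower dose.

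A second objection is that 66% rests on one value per child without covariates, while V.C plans weekly sampling and V.D plans adjustment for confounders, and both may raise power. This also stands, and 66% must not be read as the power of the planned repeated measures test. In the other direction, sampling can stop early and the power text makes no allowance for it.

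Two stronger readings are tempting, and the documents support neither:

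- *The trial is underpowered.* Step 5 shows that the power of the repeated measures analysis cannot be computed from what is given. Under some assumptions it is well above 80%, under others well below.
- *The type of SD can be inferred from the pilot.* Section I.B reports that 82% of weekly samples were below 1.35. A normal distribution with mean 1.08 and SD 0.34 puts 78.6% there. If 0.34 is the SD of child means, the share is 69–78% (assuming 4–8 samples per child and correlations from 0.3 to 0.9). The top of that range almost meets the first figure, the number of samples per child is not reported, and skew could move either figure. It settles nothing.

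**Conclusion.** The concern holds as a mismatch between the power statement and the planned tests. It is neither an arithmetic error nor a demonstrated shortfall in sample size. The 80% is the power of one unadjusted two-group comparison of single plasma selenium values. On identical inputs it is close to the omnibus figure under full effect (about 82%), too high for the omnibus test if the lower dose has half the effect (about 69%), and too high for one fully effective dose against placebo under Tukey (about 66%).

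These figures rest on a difference of 0.27, an SD of 0.34, 25 per arm, one value per child, no covariates and no losses. They cover plasma selenium only; the power text gives no figure for urinary selenium or GPx. The plan should correct this, because the stated power does not hold for the planned pairwise test on its own sizing basis and the correction costs little.

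**What to change.** In V.D, replace the sentence that states the result of the power calculation with:

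> 25 per group gives 80% power for one unadjusted two-group comparison of single plasma Se values. On the same basis the omnibus group test has about 82% power if both doses have the full effect (about 69% if the lower dose has half), and each fully effective dose against placebo under Tukey has about 66%.

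Add a clause saying whether 0.34 is the SD of single weekly samples or of child means. Then derive the power of the planned repeated measures test from the pilot data, stating the contrast, the within-child correlation and the expected number of visits. Until that is done, give no figure for the repeated measures analysis.

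The cost is one replaced sentence, one clause and one calculation from data that the sponsor already holds. No extra children are needed, and the tests do not change. The only downside is a less favourable stated power per dose.
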